2 ABBREVIATIONS AND DEFINITIONS

ADA	American Dental Association
AE	Adverse Event
AG	Attached Gingiva
ANSM	Agence Nationale de Sécurité du Médicament et des Produits de Santé
ASADE	Anticipated Serious Adverse Device Effect
BOP	Bleeding On Probing
b	buccal
CF	Consent Form
CFG	Cervical Free Gingiva
CRF	Case Report Form
CRO	Contract Research Organization
CTM	Clinical Trial Material
D	Distal
EC	Ethics Committee
eCRF	Electronic Case Report Form
FAS	Full Analysis Set
FU	Follow-up
GA	Gingival Abrasion
GCP	Good Clinical Practice
GDPR	General Data Protection Regulation
GI	Gingival Inflammation
ICH	International Council for Harmonization
IEC	Independent Ethics Committee
IP	Investigational Product
IRB	Institutional Review Board
ISO	International Organization for Standardization

ITT	Intent to treat (analysis)
IGC	Intensity of gingival coloring
L	Lingual
m	Mesial
MT	Manual toothbrush
p	Palatal
PFG	Papillary Free Gingiva
PD	Pocket Depth
PP	Per Protocol
REC	Gingival margin RECession
RIPH	Recherche impliquant la personne humaine
TEP	Time Evaluation Period
PI	Plaque index
SADE	Serious Adverse Device Effect
SAE	Serious Adverse Event
SAP	Statistical Analysis Plan
SOC	System Organ Class
SOP	Standard Operating Procedure
ST	Sonic Toothbrush
USADE	Unanticipated Serious Adverse Device Effect
UST	Ultrasonic toothbrush
ZOI	Zone Of Interest

3 PROTOCOL SUMMARY / SYNOPSIS

Study Name	ASTA
Study Title	Effects of the sonic toothbrush on the abrasion of the gingival tissue. A 3-month prospective and controlled clinical study.
Study no.	2020-A02614-35
Investigational Products:	
 • Sonicare ProtectiveClean® HX6848/92 with C2 Optimal Plaque Defense head HX9022/10 (electric toothbrush) • Pierre Fabre Inava 20/100 (manual toothbrush)
Sponsor	Philips France Commercial
Coordinating Investigator	[name], DDS, PhD Rothschild Hospital [name] [name] France
Investigational site	Hôpital Rothschild, AP-HP, Service d'Odontologie, [name], [name] France
Study type	Category 2 of Research involving human subjects (RIPH2), Post-market for a dental device (other than health products).
Methodology	
This is a randomized, monocentric, examiner-blind, two-arm, parallel, controlled clinical research study. It aims to assess gingival abrasion by the comparison of pre- to post-brushing after a single brushing and after 12 weeks of daily home brushing using a macro-relief scoring based on photographs of the gingiva. The study also aims to assess plaque removal, gingival inflammation, gingival recession and gingival color after 12 weeks. To enter the study, adult male and female subjects attending the service of dentistry at Rothschild hospital (Paris, France) will refrain from all oral hygiene procedures for 24 hours. Subjects will have the study procedure explained to them both orally and by written instructions. Eligible patients will give their written consent to participate before being included into the study. Following a baseline clinical examination for collection of the following periodontal parameters: plaque control record (PCR), bleeding on probing (BOP), gingival recession (REC), and probing pocket depths (PD), the subjects will be randomized into two balanced groups, test group assigned to the Sonicare ProtectiveClean® HX6848/92 with C2 Optimal Plaque Defense head HX9022/10 (electric toothbrush) and control group assigned to the Pierre Fabre Inava 20/100, a reference manual toothbrush. Subjects will be instructed to brush their teeth for one minute under supervision with their assigned toothbrush and a sodium monofluorophosphate (1450 ppm F) toothpaste (elmex® SENSITIVE PROFESSIONAL) with a low level of abrasion to minimize bias due to toothpaste abrasivity. After brushing, they will again be evaluated for primary and secondary outcomes (post-brushing). Subjects will be dismissed from the study site with their assigned toothbrush and toothpaste, and instructed to brush twice daily at home for the next 12 weeks. The subjects will be instructed to brush for two minutes during each tooth brushing. The subjects will report to the study site after 12 weeks of product use, at which time

Confidential

	they will be re-evaluated for gingival abrasion, as well as for plaque removal, gingival inflammation, gingival recession and gingival color. Data (photographs and clinical measurements) will be collected, i.e. primary and secondary variables of each patient, by blinded examiners.
Number of patients	30 per group, 60 in total
Visits	1. Inclusion (D1) 2. Follow-up (D90)
Primary objective and endpoint	
Primary objective
 
To compare the gingival abrasion (GA) after toothbrushing between the sonic toothbrush Sonicare ProtectiveClean® with Optimal Plaque Defense head (test group) and a conventional manual toothbrush (control group) in regular consecutive patients attending the Service of Odontology at Rothschild hospital (Paris, France)
 
Primary endpoint
 
Gingival Abrasion (GA) assessed as modification in the gingival surface based on macroscopic photographs of each gingival quadrant at each time point. Observers will score those photographs in a double-blind manner by comparing the different photographs with a photounumerical reference scale used as standard. Five parameters will be assessed on a 0-3 scale (erythema, inflammation, bleeding, recession and erosion) resulting in a 15 points scale (from 0 - no abrasion, to 15 - severe gingival abrasion).
 
Modifications in the gingival surface are defined by a macro-relief scoring based on photographs of the gingiva pre-operatively, immediately after the first brushing sequence and 90 days later

Secondary objectives and endpoints	
Secondary Objective
 
To compare :
 
 1. the plaque control 2. the gingival inflammation 3. the gingival recession 4. the gingival color 
obtained by using the sonic toothbrush Sonicare ProtectiveClean® with Optimal Plaque Defense head (test group) and by using a conventional manual toothbrush (control group) in regular consecutive patients attending the Service of Odontology at Rothschild hospital (Paris, France);
 
Secondary Endpoints
 
 1. plaque control measured by the Plaque Control Record 2. gingival inflammation measured by Bleeding On Probing 3. gingival recession defined as the distance from the cemento-enamel junction to the gingival margin and measured in millimeters using a manual periodontal probe (HuFriedy PCP UNC 15 probe, Chicago, IL, USA) 4. gingival color change based on sensory analysis.

Eligibility criteria	
Inclusion criteria
 
 1. Dentate males and females must be at least 18 years and not more than 75 years of age 2. Patient able to understand and sign the informed consent prior to starting the study 3. Patient with a minimum of 3 teeth in each of the 4 quadrants and no/or pockets >4 mm 4. Ability and willingness to comply with all study requirements. 
Non-inclusion criteria
 
 1. Pregnancy 2. Patient with cervical restorations 3. Current smoker 4. Patient with orthodontic banding 5. Patient with oral lesions or periodontal diseases 6. Patient who has been deprived of his/her freedom by administrative or legal decision or who is under trusteeship/guardianship 7. Patient already using an electric toothbrush 8. Patient with conditions or circumstances, which may prevent completion of study participation or interfere with analysis of study results, such as history of non-compliance, or unreliability; 9. Patient with non-plaque induced gingival diseases or localized gingival ulceration 10. Thin gingival phenotype 11. Patients with cardiac pacemakers to prevent any interference between the power toothbrush and the implantable cardiac device.
Method of administration	
After screening, clinical examination, informed consent collection and randomization, a blinded examiner will provide each patient a manual toothbrush or a sonic toothbrush depending on his/her allocation group (control or test group).
 
The examiner will orally explain the appropriate tooth brushing technique, the frequency and duration of tooth brushing (twice a day, 2 mins). Each participant will receive a tube of sodium monofluorophosphate (1450 ppm F) toothpaste (elmex® SENSITIVE PROFESSIONAL).
 
At the end of the study, each patient will give back the used toothbrushes and tubes of toothpaste to the blinded examiner.

Treatment scheme	
Visit 1 (V1): (D0) screening, patient's information on the study protocol, inclusion, randomization, baseline oral measurements, supply of investigational device, oral hygiene instructions, and dental photographs.
 
Visit 2 (V2): (D90) Collection and verification of investigational device, oral measurements and dental photographs.

Study Duration	Inclusion period: 6 Months

Confidential

	Total study duration: 9 Months
Study Schedule	Q2 2021 – Q1 2022
Statistical methods	
The test and control groups will be compared on the primary and secondary outcomes of the study.
 
Normality tests (e.g. Kolmogorov-Smirnov or Shapiro-Wilk test) will be used to assess the normality of the distribution. According to data distribution, t-test or Mann-Whitney u-test will be applied for continuous variables, such as the gingival abrasion and gingival relief scoring.
 
For categorical variables, Pearson's Chi square test or Fisher's Exact test will be used. Within group, tests will be used to explore the time effect, i.e. evolution between baseline and post-baseline measurements. Wilcoxon's test or Student's test for pairwise comparisons will be used, depending on the normality of the distribution.
 
A p value < 0.05 will be considered statistically significant.
 
The sample size calculation has been based on a preliminary study evaluating the primary criteria (macro-relief scoring changes between D0 and D90 after manual compared to electric brushings). In this preliminary study, we have measured a threshold value of $\Delta E = 0.67$ on the primary criteria between manual brushing and electric brushing, associated with a standard deviation of 0.84. Using a bilateral two-group test with a 0.05 two-sided significance level and a power (1-β) of 0.80 yielded a sample size of 25 subjects per group (34 subjects when considering a power (1-β) of 0.90).
 
We added 20% for potential dropouts. Thus, 30 subjects per group will be evaluated, i.e. 60 subjects will be required in total.

Visits Tasks	Screening/baseline	Follow-up
	Day 1	Day 90
Patient information and informed consent signature	X	
Inclusion/exclusion criteria	X	
Randomization	X	
Investigational device supply	X	
Plaque Control Record (PCR)	X	X
Inflammation assessment (BoP)	X	X
Gingival recession assessment (REC)	X	X
Pocket depth probing (PD)	X	X
Gingival abrasion (GA)	X	X
Gingival coloring variation assessment	X	X
Dental photograph	X	X
Oral hygiene instructions	X	
Investigational device collection		X
Assessment of toothbrush usage (patient reported)		X
Assessment of toothbrush usage (brush wear assessment)		X
Adverse events collection		X

Figure 1: Flow chart of the course of the study.

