5.1.2 Primary endpoint

Evaluation of the gingival abrasion (GA): Macro-relief scoring.

A first method for the evaluation of gingival abrasion (GA) will consist in a method of macro-relief scoring of gingival tissue as described previously by Perin *et al.* with skin tissue. This evaluation consists of acquiring macroscopic views of each investigated surface and then classifying them by observers according to a reference groups of defined abrasion intensity. This evaluation scoring,

using photo grading technique, allow delayed and blinded scoring, independent of whole-subject appearance, thus decreasing subjectivity (Perin et al., 2000).

The macro-relief gingival abrasion scoring technique consists of acquiring macroscopic photographs of each gingival quadrant at each time point. Observers will score these photographs in a double-blind manner by comparing the different photographs with a photonumerical reference scale used as standard. This scale, composed of 5 criteria each scored from 0 to 3, has already been retained by observers as being representative of the different grades of gingival abrasion. The final score will range from 0 (no abrasion) to 15 (severe gingival abrasion).

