6.6 Time and repartition of tooth brushing procedures

The randomization of the toothbrush and the brush group will be performed as previously described by the operator (see section 6.4). Subjects will receive a Sonicare ProtectiveClean® toothbrush (HX6848/92 Philips) equipped with a C2 Optimal Plaque Defense head (HX9022/10 Philips) or a standard manual toothbrush (Pierre Fabre Inava® 20/100) and a sodium monofluorophosphate (1450 ppm F) toothpaste (elmex® SENSITIVE PROFESSIONAL). The brushing duration will be inconspicuously measured in seconds with a stopwatch, while the participants are brushing. The mean duration of brushing will be 30 seconds per quadrant for manual or power brushers. All participants with their assigned toothbrush (being either the Philips Sonicare ProtectiveClean® 6809/04 or Inava® 20/100) will brush with manufacturers / professional recommendations. They will use a sodium monofluorophosphate (1450 ppm F) toothpaste. At the beginning of the study three and/or four 75 ml tubes of toothpaste will be given to each patient. It has been calculated that the dose of toothpaste per brushing was 1.21 g on average i.e. 217.8 grams for 90 days (Precisa®100C-3000D). The tubes of toothpaste are weighed at the beginning (average 108 g) and at the end of this study. It is thus possible to measure the global quantity of toothpaste used and the possible effect of this use on the surface texture of the gum tissue.

Thus, brushing time for the whole mouth will be 2 minutes for each patient from both toothbrush groups. The evaluation time and the consequences of brushing will be assessed immediately and 90 days later.

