11.5 Analysis of the primary endpoint

All parameters listed in Section 5.2.2 will be documented and compared between treatment groups.

Macro-relief scoring: The technique consists of acquiring macroscopic photographs of each gingival quadrant at each time point. Observers will score those photographs in a double-blind manner by comparing the different photographs with a photonumerical reference scale used as standard. This scale will first be retained by observers as being representative of the different grades of gingival abrasion: from 0 (no abrasion) to 15 (severe gingival abrasion) according to the following table:

Score Criteria	0	1	2	3
Erythema	None	Small (surface 0 to $\frac{1}{4}$)	Medium (surface $\frac{1}{4}$ to $\frac{1}{2}$)	Large (surface $> \frac{1}{2}$)
Inflammation	None	Small (surface 0 to $\frac{1}{4}$)	Medium (surface $\frac{1}{4}$ to $\frac{1}{2}$)	Large (surface $> \frac{1}{2}$)
Bleeding	None	Slight	Moderate	Severe/expanded
Recession	None	Small (≤ 2 mm)	Medium (3 to 5 mm)	Large (> 5 mm)
Erosion	None	Slight	Moderate	Severe/expanded

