11.8 Sample Size

The sample size calculation is based on a preliminary study evaluating the primary criteria (macro-relief scoring changes between D0 and D90 after manual compared to electric brushings). In this preliminary study, we have measured a threshold value of $\Delta E = 0.67$ on the primary criteria between manual brushing and electric brushing, associated with a standard deviation of 0.84. Using a

bilateral two-group test with a 0.05 two-sided significance level and a power (1- β) of 0.80 yielded a sample size of 25 subjects per group (34 subjects when considering a power (1- β) of 0.90).

We can add 20% for potential dropouts. Thus, 30 subjects per group is evaluated, i.e. 60 subjects are required in total.

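### The primary gingival abrasion endpoint is defined at two post-brushing times with no ranking, while the sample size rests on the D0 to D90 change alone

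*Protocol*

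**What the plan says.** Several places give the immediate and the 90-day assessment equal standing:

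- Synopsis, primary endpoint: modifications of the gingival surface are defined by "macro-relief scoring based on photographs of the gingiva pre-operatively, immediately after the first brushing sequence and 90 days later".
- Synopsis, Methodology: the aim is a "comparison of pre- to post-brushing after a single brushing and after 12 weeks of daily home brushing". On the supervised brushing at the first visit it says: "After brushing, they will again be evaluated for primary and secondary outcomes (post-brushing").
- Section 6.6: "The evaluation time and the consequences of brushing will be assessed immediately and 90 days later".

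The sample size text names one contrast. In both the synopsis (Statistical methods) and section 11.8, the primary criterion is "macro-relief scoring changes between D0 and D90 after manual compared to electric brushings".

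The two sections that should settle the matter do not. Section 5.1.2 says "The macro-relief gingival abrasion scoring technique consists of acquiring macroscopic photographs of each gingival quadrant at each time point", and section 11.5 says "The technique consists of acquiring macroscopic photographs of each gingival quadrant at each time point". Section 11.1 announces that superiority of the test group will be shown, without tying this to a time. Section 11.2 sets a two-tailed 0.05 level for all comparisons.

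**The concern.** Abrasion after one supervised brushing and abrasion after 12 weeks of home use are different questions, and a brush could do well on one and not on the other. A primary endpoint has to say which of them decides the trial. Here the definition lists both, the powering uses one, and no passage ranks them or says whether success needs either or both.

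This leaves two readings open. If a significant result at either time could be reported as the primary finding, the type I error of the claim would exceed 0.05. If both were required, type I error would not inflate, but power could fall below the planned 0.80. In addition, the label D0 in the sample size text does not say whether the pre-brushing or the post-brushing photograph of the first visit is the baseline.

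**Working it through.** **Inputs from the protocol.** Difference 0.67 and SD 0.84 for the D0 to D90 change, two-sided 0.05, power 0.80 or 0.90 (11.8); 1:1 allocation (6.4); 20% added for dropout, 30 per group (11.8). No effect size is given for the immediate change, and no correlation between the two changes.

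**1. The plan's own figure.** With n per group = 2 × [SD × (z₀.₉₇₅ + z_power) / difference]²:

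- Power 0.80: 2 × [0.84 × (1.960 + 0.842) / 0.67]² = 24.67, so 25.
- Power 0.90: 2 × [0.84 × (1.960 + 1.282) / 0.67]² = 33.03, so 34.
- 25 × 1.2 = 30.

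The stated 25, 34 and 30 reproduce. They apply to one test of the D0 to D90 change.

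**2. D90 alone.** Standardized effect 0.67 / 0.84 = 0.798; noncentral t power with 2n − 2 degrees of freedom and noncentrality 0.798 × √(n/2):

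- 30 evaluable per arm: 0.859.
- 24 evaluable per arm (30 × 0.8): 0.772.

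**3. If either time could carry the claim (a rule the protocol does not state).** Two test statistics, bivariate normal under the null, critical value 1.96. At r = 0 the two-sided chance of at least one false positive is 1 − 0.95² = 0.0975, and the chance of one in favour of the sonic brush is 1 − 0.975² = 0.0494. The correlations are assumed.

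| Correlation r | Any false positive, two-sided | False positive favouring sonic |
|---|---|---|
| 0 | 0.0975 | 0.0494 |
| 0.5 | 0.0907 | 0.0454 |
| 0.7 | 0.0835 | 0.0417 |
| 0.9 | 0.0704 | 0.0352 |
| One test only | 0.05 | 0.025 |

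**4. If both times were required (also not stated).** Power for both t-tests to be significant in favour of the sonic brush, from 100,000 simulated trials. The D90 effect is 0.798, and the immediate effect is assumed to be f × 0.798.

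| f | n = 30, r = 0.5 | n = 30, r = 0.9 | n = 24, r = 0.5 | n = 24, r = 0.9 |
|---|---|---|---|---|
| 0.5 | 0.319 | 0.328 | 0.252 | 0.272 |
| 1 | 0.771 | 0.820 | 0.647 | 0.716 |
| 1.5 | 0.858 | 0.861 | 0.766 | 0.771 |

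With an immediate effect 1.5 times the D90 effect, almost nothing is lost. With one half as large, most of the power is lost.

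**The case against.** The strongest reply is that the protocol does name its primary contrast, twice, in the sample size text. The other passages can be read as describing when photographs are taken rather than what is tested. The 3-month study title points the same way. On that reading the type I error is 0.05, the sample size is correct, and every figure in steps 3 and 4 rests on a success rule that the protocol does not contain.

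Much of this stands. D90 is the likely intention, and no error rate or power figure in the protocol is shown to be wrong. The figures are conditional and do not make the problem graver than it is. Two pieces of evidence for D90 are also weaker than they look. The single Day 1 column in the flow charts could cover photographs both before and after brushing. The visit list in section 9.3 puts photographs before the brushing session and none after it, but its order is not reliably chronological: it lists randomization ahead of the baseline measurements, which the synopsis places first.

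It could also be said that ranking time points belongs in the statistical analysis plan. That fits the handling of a secondary time point, but not the primary one. The synopsis definition explicitly includes the immediate photograph, and the Methodology text places primary outcomes at that moment. An analysis plan would have to choose between conflicting protocol statements.

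**Conclusion.** The concern holds. The primary endpoint definition and the sample size basis disagree on the primary contrast, and sections 5.1.2 and 11.5 do not resolve it. The intended answer, D90, can be recovered, so this should be fixed but does not undermine the design.

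The size is conditional. Under an either-time rule, the two-sided false-positive chance is 7.0% to 9.75% instead of 5%, and 3.5% to 4.9% instead of 2.5% in favour of the sonic brush. Under a both-times rule, power ranges from 0.32 to 0.86 with 30 evaluable per arm and from 0.25 to 0.77 with 24. These ranges rest on assumed correlations (0 to 0.9 for the first rule, 0.5 to 0.9 for the second) and an assumed immediate effect of 0.5 to 1.5 times the D90 effect.

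**What to change.** In the synopsis, section 5.1.2 and section 11.5, name one primary endpoint: the between-group difference in change in total GA score from the pre-brushing Day 1 photograph to D90, as powered in section 11.8. State that the immediate post-brushing change is secondary, either tested at 0.05 only if the D90 test is significant or reported descriptively. It would also help to show the post-brushing photograph as a separate item in section 9.3 and the flow charts, since section 9.3 lists none after the brushing session.

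The endpoint change is wording only. The sample size stays at 25 evaluable and 30 enrolled per group, and the D90 test loses neither alpha nor power. The one cost is that the immediate result can no longer carry the primary claim.

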5.2.2 Secondary endpoints

The investigator will perform the assessment of evolution of secondary objectives after 90 days, using the following endpoints:

- ✓ Comparison of gingival color;
- ✓ Presence of plaque -Plaque index, PI - (Silness and Löe, 1964)
- ✓ Presence of inflammation BOP (Ainamo and Bay, 1975)
- ✓ Presence and/or amount of gingival recession (REC).

5.2.2.1 *Changes in gingival color*

The evaluation of gingival coloring will be conducted by trained examiners and will consist in extracting each individual visual component of the gingival surface color, based on sensory analysis. This method has already been applied to describe the intensity of skin coloring (red /green/blue component) as well as luminosity, the brightness and transparency (Musnier et al., 2004) and will be applied to each subject's gingival tissue.

Photographed views will be taken according to the standard shooting protocol used in the hospital department, which ensures that all photographs are made in the axis to facilitate proper recording with minimal distortion. A control of image reproducibility will be done by an examiner with image analysis software. A previous study (Kerner et al., 2007) has shown that this method is highly correlated with clinical measurements. During photo shooting, an internal colored reference chart will be photographed in the vicinity of the photographed gingival tissue, as extensively explained by Van Poucke et al in 2010 (Van Poucke et al., 2010).

Regarding the periodontal parameters, a full-mouth examination will be performed.

5.2.2.2 *Probing pocket depth (PD)*

PD will be measured before the test/control treatment by one and the same examiner by using the PCP-UNC 15 (Hu-Friedy® Chicago, IL, USA) probe throughout the study. The probing depth will be assessed at the buccal aspects of teeth 16,14,13,11. All measurements will be adjusted to the nearest 1.0 mm.

5.2.2.3 *Gingival margin recession (REC)*

Gingival margin recession will be measured from the cemento-enamel junction to the marginal position of the gingiva with PCP-UNC 15 (Hu-Friedy® Chicago, IL, USA) probe. The measurements will be assessed at the middle of the buccal gingival recession.

5.2.2.4 *Bleeding on marginal probing (BOP)*

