6 STUDY DESIGN

6.1 Type of study

This will be a monocentric, interventional, reference-controlled, randomized, single blind, and superiority study.

The examiner will be blind regarding the investigational products.

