6.3 Treatment groups

The choice of the tooth brushing instrumentation and the brush group will be done randomly by one operator. In addition, these groups will be selected for brushing with or without instructions of the operator with manual or electric toothbrush. The Examiner will be blind and, at any stage of the measurements not informed of the distribution / repartition of the brush group / selected devices.

- ✓ Brush group 1: Sonicare ProtectiveClean® toothbrush (HX6848/92 Philips) equipped with a C2 Optimal Plaque Defense head (HX9022/10 Philips) + oral hygiene instructions + Manufacturer's instructions + sodium monofluorophosphate (1450 ppm F) toothpaste (elmex® SENSITIVE PROFESSIONAL Colgate-Palmolive) with a low degree of abrasivity.
- ✓ Brush group 2: Inava® 20/100 (Code ACL: 3401561130767) manual toothbrush + oral hygiene instructions + Manufacturer's instructions + sodium monofluorophosphate (1450 ppm F) toothpaste (elmex® SENSITIVE PROFESSIONAL Colgate-Palmolive) with a low degree of abrasivity (= 79).

1st Group: Electric toothbrush + manufacturer's instructions + professional recommendations + sodium monofluorophosphate (1450 ppm F) toothpaste (elmex® SENSITIVE PROFESSIONAL)
2th Group: Manual toothbrush + manufacturer's instructions + professional recommendations + sodium monofluorophosphate (1450 ppm F) toothpaste (elmex® SENSITIVE PROFESSIONAL)

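### The synopsis has the blinded examiner hand out the allocated brush, teach its use and take it back, which contradicts the examiner blinding in 6.1, 6.3 and 6.5 and the operator's role in 9.3 and 9.4

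*Protocol*

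**What the plan says.** The Method of administration row of the synopsis gives three tasks to the examiner:

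- Supply: "a blinded examiner will provide each patient a manual toothbrush or a sonic toothbrush depending on his/her allocation group".
- Instruction: "The examiner will orally explain the appropriate tooth brushing technique".
- Return: "each patient will give back the used toothbrushes and tubes of toothpaste to the blinded examiner".

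The Methodology row of the synopsis uses the same label for those who collect the data, namely the "primary and secondary variables of each patient, by blinded examiners". It also describes a second evaluation on Day 1, after the supervised brushing.

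The body of the protocol describes a different arrangement. Section 6.1 states: "The examiner will be blind regarding the investigational products". Section 6.3 has one operator make the random choice of brush and adds: "The Examiner will be blind and, at any stage of the measurements not informed of the distribution". Section 6.5 repeats that the examiner is blind to treatment. Section 9.3 names the operator for brush supply on Day 1 and brush collection at Day 90. Section 9.4 repeats the collection and places it once the clinical assessments are complete. Section 8.3 sets out different brushing instructions for each arm and has the investigators give them.

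**The concern.** The trial is described as examiner-blind (synopsis) and single blind (6.1). Patients know which brush they use, so the protection against biased measurement lies with the people who measure and score. The synopsis row breaks it: nobody can hand over one of two visibly different devices by allocation group, teach the technique for that device, and remain unaware of the arm.

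The readings at stake are those made at the chair. Plaque, bleeding on probing and recession all need an examiner's judgement at the site. An examiner who knows the arm could, without intending to, read them differently in the two groups.

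**Working it through.** No arithmetic applies beyond simple counts, so the check sets the passages side by side.

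**Step 1. Do the three tasks reveal the arm?**
- Supply: yes. The row itself ties the brush to the allocation group.
- Instruction: yes. Section 8.3 prescribes one technique for the electric brush and another for the manual brush.
- Return: yes. The used brush is seen. Whether this matters depends on when it happens (step 4).

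So 3 of 3 tasks are arm-revealing.

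**Step 2. What do they conflict with?**

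| Task | Synopsis row | Examiner blinding (6.1, 6.3, 6.5) | Role named in the body |
|---|---|---|---|
| Supply | blinded examiner | contradicted | operator (9.3) |
| Instruction | examiner | contradicted | investigators (8.3); 9.3 and 9.4 name nobody |
| Return of brush | blinded examiner | contradicted | operator (9.3, 9.4) |

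The conflict with the operator's role therefore covers 2 of the 3 tasks. For instruction, the conflict is with blinding only. The operator sections speak of brushes and brush heads; no section outside the synopsis names who takes back the toothpaste.

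**Step 3. Which outcomes are exposed if the dispensing examiner also measures?**
- The synopsis lists 4 secondary endpoints. Plaque, bleeding on probing and recession are read at the chair: 3 of 4.
- The fourth, colour, is taken from photographs. Section 11.6 has observers extract it in a double-blind manner, but 5.2.2.1 gives its evaluation to trained examiners. Its protection therefore also depends on keeping the roles apart.
- The primary abrasion score is graded from photographs by observers described as double-blind (5.1.2, 11.5). Section 5.1.2 adds that photo grading can "allow delayed and blinded scoring, independent of whole-subject appearance".
- Timing: the exposed readings are those after the handover, namely the Day 1 post-brushing evaluation in the synopsis Methodology row and the Day 90 visit.

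**Step 4. Does the order at Visit 2 matter?** The Treatment scheme row of the synopsis lists device collection before the oral measurements. Section 9.4 collects brushes after the clinical assessments, and the Day 90 list in 9.3 has the same order. Under 9.4 the return comes too late to influence the readings. Under the synopsis order, with an examiner receiving the brush, even someone who took no part on Day 1 could learn the arm just before measuring.

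**The case against.** The strongest defence is that this is a mislabelled role in one synopsis row. Section 6.3 cannot be met by an examiner who also dispenses, and 9.3 and 9.4 name the operator outright. If a different person measures, the chairside readings can stay blind and only the label is wrong. That much stands, and it makes the harm conditional. It does not remove the contradiction. The label occurs three times for three separate tasks, the measurers carry the same label, and no section says in terms that the person who handles the brush and the person who measures must differ. A site working from the synopsis could reasonably let one examiner do both.

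A reader might be tempted to go further in two directions that the documents do not support.

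- *That the primary endpoint is unblinded.* The protocol describes its scoring as double-blind, by observers working from photographs. It does not say that these observers are people other than the examiners, so the protection is not complete, but nothing assigns the scoring to the person who dispenses.
- *That the role conflict runs through 5.2.2, 8.4, 8.5 and 9.2 as well.* Section 5.2.2 says "The investigator will perform the assessment of evolution of secondary objectives after 90 days", but the term is generic here: 9.2 places the training of examiners and operators under a heading about investigators. Naming both groups together in 9.2 says who is trained and does not merge the roles. Section 8.4 lets any designated health professional handle dispensing and itself names the operator for reconciling the inventory. Retrieval by the site monitor in 8.5 is compatible with the operator first collecting brushes from patients.

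**Conclusion.** The synopsis row is wrong as written and should be corrected. It cannot be reconciled with examiner blinding in 6.1, 6.3 and 6.5 or, for supply and brush collection, with the operator's role in 9.3 and 9.4. This is more than a clerical matter, because following the row with the same examiner measuring would defeat the stated blinding for 3 of the 4 secondary endpoints, on Day 1 after brushing and at Day 90. It is not fatal, because the primary score is largely protected.

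The exposure rests on one assumption that the protocol neither confirms nor excludes in express words: that the examiner who handles the brush also measures. Section 6.3 points the other way. The documents give no figure from which to size a bias, so none is claimed. The different order of brush collection in the synopsis Visit 2 text and in 9.4 is a smaller, separate inconsistency that bears on the same blinding.

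**What to change.** 1. Synopsis, Method of administration: in all three sentences, replace the examiner with *the operator (not blinded)*. This agrees with 9.3 and 9.4 for brush supply and collection.
2. Section 6.5: add *Those who make the clinical measurements or score the photographs take no part in brush supply, brushing instruction, supervised brushing or brush collection.* Supervised brushing belongs in the list because watching a patient brush also shows the device.
3. Section 8.3: have the instructions given by the operator or another team member who does not measure.
4. Synopsis, Treatment scheme, Visit 2: list brush collection after the oral measurements, as in 9.4.

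Sections 8.4, 8.5 and 9.2 need no change.

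The cost is a few text edits in two synopsis rows and in 6.5 and 8.3. The main fix uses the operator role that already exists. The protocol gives no staffing numbers, so whether the separation needs an extra person at the site cannot be told from it.
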